### 6. Factors associated to grade 2-3 scintigraphy and ATTR-CM

Factors associated to grade 2 or 3 will be identified in the FAS1 by univariate and multivariate logistic regression (compared with negative patients). This analysis will be performed in the FAS1 population and will include all variables collected in the CRF for both positive and negative scintigraphy. Clinical laboratories will be excluded from this analysis as only available for positive scintigraphy. The same analysis will be repeated to identify factors associated to ATTR-CM (FAS 2 & 3).

### 7. Scintigraphy discrepancies analysis

Discrepancy in the evaluation of the scintigraphy and/or SPECT images by different evaluators will be analyzed as follow:

- Between site and 1st evaluator:

Cross tabulation between the two evaluators

Scintigraphy or SPECT images	Site evaluation				
	Grade	0	1	2	3
1 st external evaluator	0				
	1				
	2				
	3				

PFIZER CONFIDENTIAL

All percentages of discrepancies will be provided.

A weighted Kappa coefficient (measure of interrater agreement) will be provided with 95% confidence limits and exact test for the kappa coefficient.

- Between 1st and 2nd evaluators (in case there is a discrepancy between site evaluation and 1st external evaluator), same analyses will be performed.
- A listing of all individual patients will be provided for all discrepancies (site and the 2 external evaluations).

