### **9.9.4. Measurement Biases**

The assessment of the primary endpoint is based on the bone scintigraphy reading, which implies an evaluator-dependent variability and may create a bias.

In order to measure this bias scintigraphy reviews by external evaluators have been planned. Digitalized images will be reviewed by two external evaluators to analyze level of concordance/discrepancies among different specialists as part of a secondary objective for the study.

Secondary endpoints are based on laboratory analyses and may constitute a bias as each site has their own process, units and norms. They are also based on symptom assessment that may differ from an investigator to another and may constitute a bias.

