### 6.3 OTHER ENDPOINTS

#### Primary endpoint

Patients with cardiac fixation at the radionuclide bone scintigraphy and/or SPECT performed with 99mTc-DPD or 99mTc-PYP or 99mTc-HMDP will be defined as patients with a cardiac retention of grade 1, grade 2 or grade 3.

Patients without cardiac fixation at the radionuclide bone scintigraphy performed and/or SPECT with 99mTc-DPD or 99mTc-PYP or 99mTc-HMDP will be defined as patients with a cardiac retention of grade 0.

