#### Secondary endpoints

##### 1. Presence of Transthyretin amyloid (ATTR) or patients with suspicion of MGUS / Light Chain Amyloidosis (AL)

- Patients with grade 2 or 3 at scintigraphy will be considered “Cardiac amyloidosis patients”
  - Patients with grade 2 or 3 at scintigraphy without monoclonal protein abnormalities will be considered patients with **ATTR amyloidosis**
  - Patients with grade 2 or 3 at scintigraphy with monoclonal protein abnormalities will be considered of the population of **patients with suspicion of MGUS or AL amyloidosis**
- Patients with grade 1 at scintigraphy will be considered as “**undetermined**”

Monoclonal protein abnormalities are defined as patients with positive IFE (Immunofixation electrophoresis) (serum and urine) or with abnormal FLC (free light chain) ratio:

	eGFR			
	>60	45-<60	30-<45	<30
Abnormal FLC ratio	≥1.65	≥1.92	≥2.06	≥2.17
Normal FLC ratio	<1.65	<1.92	<2.06	<2.17

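### The planned reader-agreement coefficient, a four-grade weighted kappa, cannot show whether disagreements fall where they change the primary endpoint or the cardiac amyloidosis class; agreement at those two cuts should be added.

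*SAP*

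**What the plan says.** Protocol 9.9.4 recognises that the primary endpoint depends on who reads the scan. It plans external review to measure that bias, with two evaluators reading the images "to analyze level of concordance/discrepancies among different specialists". This is also a listed secondary objective.

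For site versus first external evaluator, SAP 8.2 (Other analyses, item 7) plans:

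- a four-by-four table of grades: "Cross tabulation between the two evaluators";
- percentages: "All percentages of discrepancies will be provided";
- a coefficient: "A weighted Kappa coefficient (measure of interrater agreement) will be provided with 95% confidence limits and exact test for the kappa coefficient";
- a listing: "A listing of all individual patients will be provided for all discrepancies (site and the 2 external evaluations").

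The same analyses are repeated for first versus second evaluator, but only "in case there is a discrepancy between site evaluation and" the first external evaluator. Neither the kappa weights nor the null value of the exact test is stated.

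Two endpoint definitions in SAP 6.3 dichotomise the grade. Patients with cardiac fixation (the primary endpoint) "will be defined as patients with a cardiac retention of grade 1, grade 2 or grade 3". For the first secondary endpoint, "Patients with grade 2 or 3 at scintigraphy will be considered" cardiac amyloidosis patients, and are then split by monoclonal protein findings into ATTR or suspected MGUS/AL. Grade 1 is left undetermined.

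**The concern.** The review is meant to show how far the primary endpoint depends on the reader, but the only coefficient planned is not aligned with that endpoint. One-grade disagreements differ in consequence:

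- 0/1 changes primary status and leaves the patient below the grade 2 cut either way.
- 1/2 leaves primary status unchanged and moves the patient into or out of cardiac amyloidosis. It also changes ATTR status when there is no monoclonal abnormality.
- 2/3 changes neither.

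The usual weighting schemes treat all three alike. A high weighted kappa could therefore be cited as evidence of a stable primary endpoint when it does not bear on that question.

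**Working it through.** **Stated figure.** The documents give no expected or target kappa. The nearest figure is the precision in Protocol 9.5: 1.96 × √(0.10 × 0.90 / 1500) = 1.52 percentage points. This reproduces the stated ±1.5% and serves below as a yardstick for a shift in prevalence.

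**Weights.** With four grades, linear agreement weights are 1 − |i − j|/3 and quadratic weights are 1 − ((i − j)/3)². Any one-grade disagreement earns 1 − 1/3 = 0.667 or 1 − 1/9 = 0.889, whichever boundary it crosses.

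**Assumed margins.** N = 1500, with grades 0/1/2/3 = 1275/75/60/90 for both readers. Grades 2-3 make up 150/1500 = 10%, matching the prevalence that the protocol assumes for ATTR-CM; fixation is 225/1500 = 15%. The rest of the split is my assumption.

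**Weighted kappa with 40 one-grade disagreements, 20 in each direction.** Kappa = 1 − (observed weighted disagreement)/(expected weighted disagreement).

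- Linear: observed (40/1500)/3 = 0.00889. Expected 2 × [0.85×0.05×1 + 0.85×0.04×2 + 0.85×0.06×3 + 0.05×0.04×1 + 0.05×0.06×2 + 0.04×0.06×1]/3 = 0.1826. Kappa = 0.951.
- Quadratic: observed (40/1500)/9 = 0.00296. Expected, with squared distances over 9, is 0.1453. Kappa = 0.980.

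Only the number of one-grade disagreements and the margins enter, so their location cannot matter.

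**Unweighted kappa at the cuts.** Kappa = (Po − Pe)/(1 − Pe). Where all 40 cross the cut, Po = 1460/1500 = 0.9733.

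- 0 vs 1-3: Pe = 0.85² + 0.15² = 0.745; kappa = 0.2283/0.255 = 0.895. Positive agreement 2×205/450 = 0.911; negative 2×1255/2550 = 0.984.
- 0-1 vs 2-3: Pe = 0.90² + 0.10² = 0.82; kappa = 0.1533/0.18 = 0.852. Positive agreement 2×130/300 = 0.867; negative 2×1330/2700 = 0.985.

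| All 40 at | Weighted kappa, linear / quadratic | Kappa 0 vs 1-3 | Kappa 0-1 vs 2-3 |
|---|---|---|---|
| 0/1 | 0.951 / 0.980 | 0.895 | 1.000 |
| 1/2 | 0.951 / 0.980 | 1.000 | 0.852 |
| 2/3 | 0.951 / 0.980 | 1.000 | 1.000 |

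**A one-way shift.** Take the same site margins. The evaluator reads 50 site grade 1 scans as 0, 20 site grade 2 scans as 1, and 10 site grade 1 scans as 2. Fixation prevalence is 225/1500 = 15.0% by site and 175/1500 = 11.7% by evaluator. The 3.3-point gap is about twice the stated precision, and also exceeds the half-width at 15% prevalence, 1.96 × √(0.15 × 0.85 / 1500) = 1.8 points. Weighted kappa is still 0.897 (linear) or 0.958 (quadratic). Kappa at 0 vs 1-3 is 0.856, and positive agreement is 2×175/(225 + 175) = 0.875.

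**The test.** If its null is kappa = 0, which is an assumption, the large-sample z in the three tabulated cases is 43.8 (linear) or 37.9 (quadratic). Rejection would say nothing about whether agreement is adequate.

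**The case against.** The strongest reply is that the plan already reports the facts. The 4×4 table shows the 0/1 and 1/2 cells, the percentages and listing report discrepancies directly, and the table margins show any prevalence shift. A reader might infer that agreement is reduced to a single kappa that conceals endpoint-changing disagreements. The SAP does not support that: both dichotomised kappas can be derived from the planned table.

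Three other tempting readings also fail.

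- That the study uses the grade only through two cuts. SAP 5.1 compares grade 1 with grades 2 and 3, SAP 6.4 lists the four grades as a covariate, and variables are described by single grade. An ordinal coefficient is therefore a legitimate analysis.
- That one-step disagreements get near-full credit. That fits quadratic weights (0.889) but not linear ones (0.667), and the SAP names neither.
- That weighted kappa must mask trouble at both cuts. In an assumed 1000-scan table (evaluator rows by site columns: 800,40,0,0; 10,10,5,0; 0,5,45,5; 0,0,5,75), kappa at 0-1 vs 2-3 is 0.957 against 0.958 quadratic and 0.896 linear. The shortfall appears only at 0 vs 1-3, where kappa is 0.827.

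The test carries no decision either, since SAP 4.1 and 4.2 disclaim inferential hypotheses and call all tests exploratory.

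What remains is narrower. Raw percentages in a mostly grade 0 sample are not chance-corrected, have no stated interval and do not isolate agreement on positives. If the weights and any dichotomised results are not prespecified, they can be chosen after the data are seen.

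**Conclusion.** The point holds as a gap in the choice of summary statistic. The planned coefficient cannot distinguish disagreements that alter the primary endpoint or cardiac amyloidosis class from those that alter neither. In the equal-margin illustration it stays at 0.951 or 0.980 while kappa at the affected cut ranges from 0.852 to 1.000.

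The equal credit for one-grade disagreements follows from the weights and needs no assumed data. The exact invariance also requires the same reader margins across tables. The sizes rest on assumed tables, because the documents give neither a grade distribution nor a disagreement rate; they show what can happen, not what is expected. The objective is secondary and descriptive, and the primary prevalence estimate is not invalidated. This is a worthwhile improvement at almost no cost.

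**What to change.** In SAP 8.2, Other analyses, item 7:

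- Keep the 4×4 table, percentages, listing and weighted kappa, and name the weights.
- For site versus first evaluator, prespecify unweighted kappa, positive agreement and negative agreement, each with a 95% CI, at 0 vs 1-3 and at 0-1 vs 2-3.
- Report fixation prevalence by each reader alongside, because these agreement measures do not show the direction of a shift.
- State the null of the exact test. If it is kappa = 0, drop the test or say that it does not address adequacy of agreement.

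The additions are confined to site versus first evaluator because the second comparison covers only scans already in dispute, so a kappa there would not estimate agreement in FAS1.

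The cost is a few lines of SAS on a table already planned, with no new data. The reported agreement may look less favourable than the weighted kappa alone.

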### **9.2.3. Centralized Review of Bone Scintigraphy (for all patients)**

In this study, all the scintigraphy/SPECT tests will be additionally reviewed by two external evaluators.

The objective of this evaluation will be to assess the level of discrepancy in the evaluation of the scintigraphy/SPECT images by different evaluators

All the scintigraphy/SPECT tests will be uploaded in a dedicated database via the study web site.

Two experts from the scientific committee members will connect to the study web site with personalized connection access. They'll review the scintigraphies/SPECT and enter their evaluation.

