### **ANNEX 3 – SCINTIGRAPHY EXTERNAL REVIEW**

In this study, all the scintigraphy tests will be additionally reviewed by two external evaluators.

The objective of this evaluation will be to assess the level of discrepancy in the evaluation of the scintigraphy or SPECT images by different evaluators

All the scintigraphy tests will be uploaded in a dedicated database via the study web site.

Two experts from the scientific committee members will connect to the study web site with personalized connection access. They'll review the scintigraphies and enter their grading evaluation.

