### Analysis of primary and secondary objectives

For each objective, a percentage/prevalence with its 95%CI will be assessed overall and in the sub-groups defined in section 5.3 if pertinent.

Endpoints	Population or Subgroup
Percentage of patients with cardiac fixation at the radionuclide bone scintigraphy and/or SPECT performed with 99m Tc-DPD or 99m Tc-PYP or 99m Tc-HMDP among patients with (left ventricular hypertrophy) LVH from an undiagnosed etiology	FAS1
Prevalence of Transthyretin amyloid (ATTR) or patients with suspicion of MGUS / AL amyloidosis	FAS1
Prevalence of hereditary (ATTRv) and wild-type (ATTRwt) ATTR amyloidosis in patients with positive scintigraphy	FAS2 & 3 (including 3.1 and 3.2)
Prevalence of TTR genetic mutation in patients with positive scintigraphy	FAS2 & 3 (including 3.1 and 3.2)
Prevalence of patients with familial history of known cardiomyopathy (CM), polyneuropathy (PN), sudden cardiac death (SCD) among their relatives (parents, siblings and 2 nd /3 rd grade family)	FAS1, 2 & 3 (including 3.1, 3.1(ATTRv), 3.1(ATTRwt) and 3.2)
Prevalence of patients with Senso-motor Polyneuropathy	FAS2 & 3 (including 3.1, 3.1(ATTRv), 3.1(ATTRwt) and 3.2)

PFIZER CONFIDENTIAL

Endpoints	Population or Subgroup
Prevalence of patients with CTS	FAS2 & 3 (including 3.1, 3.1(ATTRv), 3.1(ATTRwt) and 3.2)
Prevalence of patients with autonomic dysfunction	FAS2 & 3 (including 3.1, 3.1(ATTRv), 3.1(ATTRwt) and 3.2)
Prevalence of patients with cardiological manifestations	FAS2 & 3 (including 3.1, 3.1(ATTRv), 3.1(ATTRwt) and 3.2)
Prevalence of patients with laboratory signs	FAS2 & 3 (including 3.1, 3.1(ATTRv), 3.1(ATTRwt) and 3.2)
Description of the clinical and biochemical characteristics between patients with positive scintigraphy (cardiac fixation at the bone scintigraphy grade 1, 2 or 3) and/or SPECT (See section 0 § 3).	FAS2 & 3 (including 3.1, 3.1(ATTRv), 3.1(ATTRwt) and 3.2)
Discrepancy in the evaluation of the scintigraphy and/or SPECT images by different evaluators (See section 0 § 7)	FAS1

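### Agreement between the two external readers is to be computed only on scans where the site and reader 1 disagree, so that kappa does not measure how well the two experts agree

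*SAP*

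**What the plan says.** SAP section 8.2, Other analyses, item 7 has three parts:

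- **Site versus first external evaluator.** A 4 × 4 table of grades, the discrepancy percentages and a kappa, with no restriction on scans: "A weighted Kappa coefficient (measure of interrater agreement) will be provided with 95% confidence limits and exact test for the kappa coefficient". The weighting scheme is not given.
- **First versus second external evaluator.** Here "same analyses will be performed", but under a condition in brackets: "in case there is a discrepancy between site evaluation and" the first external evaluator.
- **A patient listing** of discrepant cases, showing the site grade and both external grades.

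The endpoint table earlier in section 8.2 gives FAS1 as the population for the discrepancy endpoint and refers to this item for the method.

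The Protocol describes an unrestricted double reading. Section 9.2.3 says that "all the scintigraphy/SPECT tests will be additionally reviewed by two external evaluators", and Annex 3 repeats it: "all the scintigraphy tests will be additionally reviewed by two external evaluators". Section 9.9.4 gives the reason. The primary endpoint depends on the reader, so the images "will be reviewed by two external evaluators to analyze level of concordance/discrepancies among different specialists". The SAP's revision table records that a discrepancy analysis was added in version 2, but not that the expert comparison is limited to a subset.

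**The concern.** The bracketed condition selects scans by an event that involves reader 1's own grade. Scans that the site and reader 1 graded alike are dropped. Those are mostly the clear scans, on which reader 2 would usually agree as well. The scans that remain are ones where the site or reader 1 erred, and the share due to reader 1 depends on how accurate reader 1 is relative to the site.

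A kappa on that subset therefore mixes expert agreement with site quality. With the experts unchanged, it rises as the sites get worse. It would also be the only planned figure for agreement between the two experts, and a low value could be misread as showing that specialists grade these scans inconsistently.

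If the bracket instead means that reader 2 adjudicates conflicts, kappa is not the right summary, and the SAP does not say that it departs from the double reading in the Protocol.

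**Working it through.** The documents state no target kappa, expected agreement or sample size for this analysis, so there is no planned figure to reproduce. The check has to show what the selection does.

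**Inputs.** From the documents: four grades (0 to 3), weighted kappa, about 1500 patients planned (Protocol 9.1), and 1000 screened as a stopping point in the abstract's milestones. Assumed, because the documents do not give them: grade mix, reader error and site error.

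**Step 1: raw agreement by hand.** Let each expert grade correctly with probability *e* and the site with probability *s*. Errors go to the adjacent grade and are independent given the true grade. For grades 0 and 3, which have one adjacent grade:

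- P(site ≠ R1) = *e*(1 − *s*) + *s*(1 − *e*)
- P(site ≠ R1 and R1 = R2) = *e*²(1 − *s*) + *s*(1 − *e*)²

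With *s* = *e*, the second is *e*(1 − *e*) and the first is 2*e*(1 − *e*). Their ratio is 1/2 **whatever the value of *e***. Equally skilled readers therefore show about 50% expert agreement in the subset, however good they are. Over all scans the same experts agree with probability *e*² + (1 − *e*)², which at *e* = 0.95 is 0.9025 + 0.0025 = 0.905.

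With *e* = 0.95 and *s* = 0.85, the subset figure is (0.1354 + 0.0021) / (0.1425 + 0.0425) = 0.1375 / 0.185 = 0.74. The experts have not changed; only the sites got worse.

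**Step 2: kappa by exact enumeration.** Same model, all four grades, linear weights, kappa = (observed − expected) / (1 − expected) on weighted agreement. Take 90% grade 0 (mix 90/3/3/4) and all readers 95% accurate:

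- All scans: (0.968 − 0.849) / (1 − 0.849) = 0.79
- Subset: (0.833 − 0.758) / (1 − 0.758) = 0.31

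The subset holds 9.5% of scans, about 143 of 1500. Letting the common accuracy run from 0.85 to 0.98 moves the all-scan kappa from 0.54 to 0.91, while the subset kappa stays at 0.30 to 0.31.

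**Step 3: varying site quality.** Latent uptake = true grade + uniform(−0.5, 0.5). Each expert adds normal noise with standard deviation *sd*, the site adds *m* times that, and the result is rounded to 0–3. Grade mix 80/5/5/10, linear weights, 400 runs of 1000 scans:

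| Site noise ÷ expert noise (*m*) | 1 | 1.5 | 2 | 3 | 5 |
|---|---|---|---|---|---|
| *sd* 0.1, R1–R2 all scans | 0.92 | 0.92 | 0.92 | 0.92 | 0.92 |
| *sd* 0.1, R1–R2 subset | 0.47 | 0.57 | 0.66 | 0.76 | 0.84 |
| *sd* 0.1, subset size per 1000 | 62 | 79 | 98 | 139 | 220 |
| *sd* 0.1, site–R1 all scans | 0.92 | 0.90 | 0.88 | 0.83 | 0.74 |
| *sd* 0.4, R1–R2 all scans | 0.71 | 0.71 | 0.71 | 0.71 | 0.71 |
| *sd* 0.4, R1–R2 subset | 0.45 | 0.54 | 0.59 | 0.62 | 0.64 |

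A repeat with one million scans per cell agreed to about 0.01. The ranking can reverse: a 0.71 pair with the poorest sites scores 0.64, above a 0.92 pair with good sites at 0.47.

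**Step 4: other settings.** Over two grade mixes and two error models, the loss in kappa is 0.25–0.46 with equal readers, 0.12–0.31 with sites at twice the experts' error, and 0.00–0.14 at five times. If the two experts share part of their error (all-scan kappa 0.92–0.94), the subset gives 0.65–0.89. With quadratic weights, mix 80/5/5/10 and *sd* 0.1, 0.97 falls to about 0.70 with equal readers and 0.92 at five times.

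**The case against.** The bracket can be read as a trigger: if any discrepancy turns up, compare the two experts on all scans. The FAS1 entry fits that reading. But with about a thousand scans some discrepancy is almost certain, so the condition would then do nothing. The scan-by-scan reading is the natural one, and at best the text needs clarifying.

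The Protocol (section 9.7) lets the SAP modify its plans and requires an amendment only for major changes to the primary endpoint. That is true, and it weakens any complaint about procedure. It does not make the subset kappa an estimate of expert agreement.

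The SAP states the condition openly, and the comparison closest to the primary endpoint, site versus reader 1, is unrestricted. Both points stand and limit the weight of the concern. Section 9.9.4 nevertheless names concordance among specialists as a purpose of the double reading.

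The size, and at the extreme the direction, depend on the model. With 10% expert error and adjacent-grade misgrading (mix 80/5/5/10), the loss almost vanishes at 50% site error (0.780 against 0.777) and reverses at 80% (0.780 against 0.844). The ranking reversal is also a corner case: the site versus reader 1 kappa would be about 0.28 in one study and 0.92 in the other, and the unrestricted first table would show it. These points rule out quoting one figure for the bias, but leave the selection problem in place.

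**Conclusion.** The concern holds. As written, the expert-versus-expert kappa is computed on a subset chosen partly by reader 1's own errors and does not estimate agreement between the two experts over FAS1. In the settings examined it is too low by up to 0.46 on the kappa scale. The loss shrinks towards zero as the sites become much worse than the experts, and the sign changed only at 80% site error. These sizes rest on assumed grade mixes, error models and site quality. That the figure depends on site quality follows from the selection itself.

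The prevalence estimate, the diagnostic classification, the regressions and the site versus reader 1 kappa are untouched. The SAP should be corrected, at the modest weight of one part of a descriptive secondary objective.

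**What to change.** **If reader 2 read all scans, as the Protocol states:** remove the bracketed condition. Produce the table, discrepancy percentages and weighted kappa for reader 1 versus reader 2 on all FAS1 scans with both readings. Add the same for site versus reader 2; this is not needed to cure the flaw, but it completes the three pairs. Show the scans where the site and reader 1 differ as a separate adjudication table or listing, without kappa. State the kappa weights (linear or quadratic) at the same time.

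**If reader 2 read only discordant scans:** drop the reader 1 versus reader 2 kappa, because all-scan expert agreement cannot then be estimated. Report how often reader 2 sided with the site, with reader 1 or with neither, and state the departure from Protocol section 9.2.3 and Annex 3.

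**Cost:** SAP wording and two extra tables in the first case; one kappa dropped, a short tabulation and a sentence added in the second. Neither needs new readings.
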